5.9 Statistics

Analysis will be performed by a member of the Geisinger Biostatistics Core.

5.9.1 Statistical Analysis Plan

Randomization scheme: The randomization scheme will be stratified on the potential study participant's most recent HbA1c value (< 6.5% vs \geq 6.5%).

Analysis methods: Descriptive statistics and plots for each variable will be inspected to identify influential points and to assess normality. Non-normally distributed variables will be transformed (e.g., logarithmic) as appropriate for parametric analysis, otherwise non-parametric methods will be used. Means, standard deviations, medians, ranges (maximum/interquartile) and 95%

confidence levels will be calculated for baseline outcome variables (HbA1c, LDL-C, systolic blood pressure) for the entire group, and stratified by CHIP vs. control group. The difference in outcomes will be calculated and treated as dependent variables. Since this is a pilot study the focus of the analysis will be estimating the mean and standard deviation of the change at 3- and 6-month for each primary and secondary outcome. We will also estimate the difference of the changes between groups and the variability. These estimates will then be used to design a larger scale study that will seek external funding. All estimates will be calculated under the ‘intent-to-treat’ principle. We will also collect and report on the proportion of individuals contacted and consent to participate, and compliance on attending the CHIP session. For those individuals contacted and do not agree to participate, we will collect the reason (e.g., not interested, lack of access to transportation, lack of internet, not able to reach).

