- Biometric, biomarker, and medication data will be collected by the study team at the Miller Center or biomarkers may be collected at a Geisinger lab. Baseline appointments will be offered before and after the first scheduled class and 3-month data collection will occur the week of the final class. Data collection at 6-months will occur at appointments scheduled individually with participants. Participants will complete the Wellbeing360 survey through CHIPHub. They will be given as much time as they need to complete the survey. Study staff will make up to three reminder calls to participants around the time they are due for each survey to encourage them to complete the surveys and assist with any technical difficulties. Data will be uploaded to the Lifestyle Medicine Institute's HIPAA-compliant servers, with the raw data transferred to secure Geisinger servers within one week. Medication lists will be determined based upon a medication reconciliation process which will begin by asking each participant what medication he or she takes. If a participant is not confident of his or her medication list, a study team member will obtain the medication list from the patient's primary care office and/or review the patient's chart in Epic to confirm medication list accuracy. The study team will obtain permission to access medication information for patients who are not seen within the Geisinger system. For participant with complex medication lists, or those which for any reason cannot be reconciled/entered into the database within the span of a standard biometric/biomarker appointment, the study team will prioritize collection of biomarkers and biometrics during the in-person encounter, as these need to be collected in-person and are especially time sensitive. For medication reconciliation and data entry

which requires more time with the participant, or guidance from the study physician, a study team member will follow up over the phone.

- Control arm subjects will have the same measures collected with the same protocols at the Miller Center at private appointments at baseline, 3-months and 6-months and the biomarkers for the control group may also be collected at a Geisinger lab.

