5.7 Primary Endpoints

Clinical endpoint: Change in HbA1c at 6 months compared to baseline.

Feasibility endpoint: What proportion of individuals contacted agree to participate; what proportion of participants complete the intervention; what proportion of individuals contacted are excluded from the study based on lack of access to transportation or internet.

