5.9.2 Statistical Power and Sample Size Considerations

Using published data from Vanderbilt our study would require almost 300 participants per group. However, since this will be a new endeavor at The Miller Center and with the adaptations to the CHIP protocol, we have decided our best initial step is to conduct a pilot study to work out the process of offering this program and recruiting subjects. Therefore, for the pilot study we are interested in the variability of the estimates needed to design a larger scale study. With 30 participants per group the study is able to estimate the 95% confidence interval of mean change in HbA1c (or any of the other change variables) with a half-width of 0.37 of the standard deviation of the change. Also, with 30 participants per group, the study is able to estimate the 95% confidence interval of the difference in change in HbA1c with a half-width of 0.52 of the standard deviation of the change. This will provide us with a range of possible values for future sample size calculations.

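### The arms are compared on raw change scores; adjusting for the baseline already collected would usually give a narrower interval at almost no cost

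*Combined protocol and SAP*

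**What the plan says.** The primary clinical endpoint in section 5.7 is "Change in HbA1c at 6 months compared to baseline". For the analysis, section 5.9.1 states "The difference in outcomes will be calculated and treated as dependent variables" and, for the comparison of arms, "We will also estimate the difference of the changes between groups and the variability". The purpose follows: "These estimates will then be used to design a larger scale study that will seek external funding".

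The same section stratifies randomisation on the latest HbA1c on file, below 6.5% against 6.5% or above ("The randomization scheme will be stratified on the potential study" opens that sentence). Neither this stratum nor the baseline value of any outcome is named as a covariate anywhere in the document. Adjustment is not ruled out either.

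Section 5.9.2 gives the expected precision of the between-arm difference, with 30 per arm, as a 95% interval "with a half-width of 0.52 of the standard deviation of the change".

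The baseline data exist in both arms. Section 5.6 says "Control arm subjects will have the same measures collected with the same protocols", at baseline, 3 months and 6 months.

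**The concern.** When change is analysed with no covariate, baseline enters only through the subtraction, so its coefficient is fixed at 1. That matches the efficiency of an estimated slope only when the true slope of follow-up on baseline is close to 1. If the slope is lower, as it is when values regress toward the mean, the change score carries baseline noise that a regression would remove.

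The between-arm difference and its variability are the pilot's stated inputs to the next trial. A wider interval than the data require is an avoidable loss. In addition, the planned summaries would not let a reader size a baseline-adjusted trial: the baseline SD and the SD of change do not by themselves determine the residual SD, since the follow-up SD and the correlation are both unknown.

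**Working it through.** **Inputs.** From section 5.9.2: 30 per arm, 95% two-sided intervals, and stated half-widths of 0.37 (one arm) and 0.52 (difference) SD of change. Not in the documents and therefore varied: r, the correlation of baseline with follow-up, and k, the follow-up SD divided by the baseline SD. All 60 participants are taken to have data.

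**The plan's own figures.**
- One arm: t(29)/√30 = 0.373, which rounds to 0.37.
- Difference: t(58) × √(2/30) = 0.517, which rounds to 0.52.

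Both reproduce, and both are for unadjusted change.

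**Effect of estimating the slope.** Take the baseline SD as 1.
- Variance of change: 1 + k² − 2rk.
- Residual variance after regression on baseline: k²(1 − r²).
- Difference between the two: (1 − rk)². This is never negative and is zero only when the slope rk equals 1.

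The variance ratio is v = k²(1 − r²)/(1 + k² − 2rk), which reduces to (1 + r)/2 when k = 1. Allowing for the lost degree of freedom and for chance baseline imbalance, the adjusted half-width is t(57) × √[(2/30) × v × (1 + 1/56)].

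Example, k = 1 and r = 0.5: v = 0.75, half-width 0.452, and 0.452/0.517 = 0.874, so 12.6% narrower.

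Adjusted half-width in SD of change, against 0.517 unadjusted:

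| k | r = 0.5 | r = 0.7 | r = 0.8 | r = 0.9 |
|---|---|---|---|---|
| 1.0 | 0.452 | 0.481 | 0.495 | 0.508 |
| 1.2 | 0.487 | 0.513 | 0.521 | 0.516 |
| 0.8 | 0.394 | 0.413 | 0.417 | 0.407 |

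Worst case, slope exactly 1 (v = 1): 0.522, or 0.9% wider.

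**Simulation of the full model (arm, baseline, stratum).** 3,000 trials of 60 people in each of 12 settings. Assumed: HbA1c on file with mean 7.4 and SD 1.3, correlated 0.8 with measured baseline, and blocks of 4 within stratum. Change in mean half-width relative to unadjusted change:

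| k | r = 0.5 | r = 0.7 | r = 0.8 | r = 0.9 |
|---|---|---|---|---|
| 1.0 | −12.6% | −7.0% | −4.2% | −1.6% |
| 1.2 | −5.8% | −0.7% | +0.9% | −0.2% |
| 0.8 | −23.6% | −20.4% | −19.3% | −21.1% |

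Coverage of the 95% interval was 0.945 to 0.968 unadjusted and 0.943 to 0.953 adjusted. The mean error of every estimate was within 0.007 SD of change. Once baseline is in the model the stratum adds no precision: at k = 1 and r = 0.8 it moves the half-width from 0.492 to 0.494.

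**How often a single trial gains.** In a separate simulation (10,000 trials per setting, k = 1, unstratified), the baseline-adjusted interval was the narrower one in 99%, 94%, 85%, 63% and 46% of trials at r = 0.5, 0.7, 0.8, 0.9 and 0.95.

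**The case against.** The strongest reply is that nothing here is an error. Endpoint, analysis and stated precision are all in terms of change and agree with one another. The pilot's stated focus is each arm's mean change and its SD, and section 5.9.2 already says that a powered comparison would need nearly 300 per arm. Moving a half-width from 0.52 to about 0.49 alters no pilot decision. The records are kept (section 5.10.1), so the residual SD and r can be computed later. Sizing an adjusted trial from the SD of change makes it too large, not underpowered. All of this stands, and it limits the weight of the point.

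The wording could also accommodate a regression of change on arm and baseline, which gives the same arm effect as regressing follow-up on them. That is true, but no covariate is written, and the 0.52 is the unadjusted figure.

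Two numerical objections stand in part:
- The gain depends on an unknown r and k. For outcomes that track very closely it can vanish: at r = 0.95 with equal SDs the interval is only 0.3% narrower.
- For HbA1c, stratified randomisation already balances part of the baseline, so the unadjusted interval is somewhat conservative and interval width overstates the real gain. Under the stratified design with k = 1, two further sets of simulations put the fall in the actual SD of the estimate at about 8 to 10%, 5%, 3% and at most 1% for r = 0.5, 0.7, 0.8 and 0.9. At k = 0.8 one of them gave 14 to 18%, against 19 to 24% in width.

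Neither overturns the claim that the reported interval would usually be narrower.

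**Conclusion.** The concern holds, as a recommended improvement and not as the correction of an error. The planned comparison is unbiased, its interval is valid, and the 0.37 and 0.52 are right for it. Adjustment narrows the interval by between about a quarter (follow-up SD 0.8 times baseline) and nothing, and widens it by about 1% at worst, when the slope is near 1. With equal SDs and r = 0.8 the gain is about 4%.

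These sizes assume 30 per arm with complete data, approximate normality, a common slope in both arms, and values of r and k that the documents do not supply. The harm of leaving the plan as it is would be modest, but the trade favours adjustment, and it serves the pilot's stated purpose of informing a larger study.

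**What to change.** In section 5.9.1, for continuous outcomes measured at baseline and follow-up in both arms (HbA1c, LDL-C, blood pressure, weight and BMI, waist circumference, Wellbeing360):

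- Estimate the 3- and 6-month between-arm difference from a linear model with arm, the baseline value of that outcome, and the HbA1c randomisation stratum (<6.5% vs ≥6.5%). The stratum is there to match the randomisation, not to gain precision.
- The plan provides that "Non-normally distributed variables will be transformed (e.g., logarithmic) as appropriate for parametric analysis, otherwise non-parametric methods will be used". Where a transformation is used, apply it to baseline and follow-up alike.
- Report the adjusted difference with its 95% interval, the residual SD, and the correlation of baseline with follow-up.
- Keep the planned mean and SD of change by arm. The endpoint in section 5.7 need not change.

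Attendance (no baseline or control value), medication counts, costs, and outcomes sent to non-parametric methods fall outside this change. The 0.52 in section 5.9.2 can stay if it is labelled as the figure for unadjusted change.

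The cost is a few lines of SAP text and code and one or two degrees of freedom, with an interval about 1% wider if the true slope is near 1. No new data are needed.

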5.9.2 Statistical Power and Sample Size Considerations

Using published data from Vanderbilt our study would require almost 300 participants per group. However, since this will be a new endeavor at The Miller Center and with the adaptations to the CHIP protocol, we have decided our best initial step is to conduct a pilot study to work out the process of offering this program and recruiting subjects. Therefore, for the pilot study we are interested in the variability of the estimates needed to design a larger scale study. With 30 participants per group the study is able to estimate the 95% confidence interval of mean change in HbA1c (or any of the other change variables) with a half-width of 0.37 of the standard deviation of the change. Also, with 30 participants per group, the study is able to estimate the 95% confidence interval of the difference in change in HbA1c with a half-width of 0.52 of the standard deviation of the change. This will provide us with a range of possible values for future sample size calculations.

5.10 Data Management

5.10.1 Data Collection and Storage

Potential participants will be identified by a GHP data broker from an institutional data warehouse. The list of GHP members, including data relevant to recruitment contact (name, address, phone number, etc.) and most recent HgA1c will be provided to the study team.

A PACDC broker will create and maintain a database for project tracking in a secure Research Electronic Data Capture system (REDCap). This electronic data will be stored on Geisinger's secure network and will house recruitment and study data. The database will contain Protected Health Information (PHI) elements, such as name, date of birth, medical record number, and date of consent. Only IRB-approved study team members authorized by the PI will have access to this database and data collected for this research. These records will be kept indefinitely as communicated to patients and described in the informed consent form. Any data transmitted externally will be consistent with data sharing language included in applicable agreements.

- The research team may perform manual chart reviews to access any required data elements that are not available through the initial data pull and to verify data from the initial data pull.
- Biometric data will be obtained and recorded by a designated member of the study team and transcribed into the secure study database.
- CHIP metrics (e.g., attendance, engagement, etc.) will be tracked by the Miller Center staff and housed in a secure database.
- Surveys may be administered online or by paper. CHIP Lifestyle Medicine, proprietors of the CHIP program, will collect the Wellbeing360 data. This survey information will be entered and housed in the secure REDCap database.

The following data, including relevant dates, will be collected:

- Name
- Medical record number (if a participant does not have a Geisinger medical record number, we will create one to allow for lab testing)
- Address
- Phone number
- Email address
- Primary Provider Affiliation
- Lab values

- Baseline demographic variables of patients (age, sex, ethnicity, tobacco use, comorbidities)
- Biometrics (including height, weight, BMI, waist circumference, and blood pressure)
- Psychometrics: Wellbeing360 data
- Current medications
- GHP claims data (including number of claims and total cost of inpatient, emergency department, outpatient encounters, etc)

5.10.2 Records Retention

Records of data generated in the course of the study and maintained by the study team shall be retained for at least 6 years and could be used for future research studies submitted and approved by the IRB.

6 SAFETY MONITORING

6.1 Adverse Event Reporting

Not applicable for this minimum risk study.

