 - Participants will be sent the menu for meals associated with all sessions at the start of the class. When participants cannot attend due to pandemic restrictions, or if they choose to attend a meeting virtually, they will be encouraged to buy their own ingredients and prepare the same meal they would have been served on site at the Miller Center. Participants will be encouraged to prepare the meal before the class, post photographs and communicate via discussion board and/or video chat. The meeting can include discussion of participants' experience cooking.
 - The same interactive lectures used for in-person meetings will be used for virtual meetings.

Additional procedures for the hybrid online/in-person approach will be as follows:

- Participants will be asked to enroll only if they can make a good faith effort to attend at least 80% of classes live (in-person or online) and to watch classes they miss within one week of the live event
- Participants will be expected to attend in person at the Miller Center twice weekly for the first month, practicing appropriate social distancing measures as may be necessary at the time of this event. After the first month, they will have the option of attending either in-person at the Miller Center or over Microsoft Teams for all subsequent classes except for the final class.
- All classes can be moved to a mandatory online format in case of inclement weather and/or if current public health recommendations preclude in-person classes from being held. The facilitators will lead all classes from meeting spaces at the Miller Center. This decision to alter format due to weather or pandemic concerns will be made at the discretion of the Miller Center director
- Participants will be disenrolled from the program if they request to be removed from the study (e.g. if they withdraw consent, if they move out of the area). The study doctor could decide to disenroll participants from this research study if they believe it is in the participant's best interest, if a participant had two consecutive HbA1c results less than 6.5% while off all diabetes medications, if a participant does not follow the study direction, if a participant is not able to attend the required classes, or for any other reason

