5.8 Secondary Endpoints

- HbA1c control at 3 months
- LDL-C at 3 and 6 months
- Biometrics at 3 and 6 months: weight, body mass index, blood pressure
- Psychosocial/behavioral: Wellbeing360 at 3 and 6 months
- Health behaviors, as measured by CHIP participation: overall program completion, attendance stratified by in-person versus online, proportion of required in-person visits attended
- Number of diabetes medications prescribed at 3 and 6 months
- Total cost of care over 6 months and comparison of total cost of care over the same 6 months the year prior and the 6 months immediately leading up to the study start date.

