8 PROTECTION OF HUMAN SUBJECTS

8.1 Informed Consent and HIPAA Authorization

The investigator will provide for the protection of the subjects by following all applicable regulations. The informed consent/authorization form will be submitted to the IRB for review and approval.

Before any procedures specified in this protocol are performed, a subject must:

- Be informed of all pertinent aspects of the study and all elements of informed consent.
- Be given time to ask questions and time to consider the decision to participate.
- Voluntarily agree to participate in the study.
- Sign and date an IRB-approved informed consent form.

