8.2 Protection of Human Subjects Against Risks

Risk of Loss of Confidentiality

There is a risk of loss of confidentiality. In order to minimize that risk, all electronic study data will be kept in password-protected computer files, and hard copy data will be stored in a locked environment that is only accessible only to the study team members. Data will be coded by assigning a unique study identification number to each participant. Analysis will be performed using the coded data. Only aggregate data without personal identifiers will be included when presenting results or submitting manuscripts for publication.

Blood Draw Risk

Providing blood samples via venipuncture can pose a minimal risk to participants. Individuals may feel faint, experience mild pain, bruising, irritation or redness at the site of puncture. In rare cases, an infection could develop.

Risk of Low Blood Sugars or Low Blood Pressures

Patients in this study will have type 2 diabetes (which is associated with hypertension), and they may be on medications for diabetes and/or blood pressure which have the potential to overshoot and cause low blood sugars and/or low blood pressures. Intensive therapeutic lifestyle change through CHIP may help to control blood sugars and blood pressures. This may increase patients' risk of medication-associated low blood sugars and/or low blood pressures, especially if patients do not adjust their medications to account for the effects of CHIP. Patients will be advised to discuss their CHIP participation with their primary care providers and to assess with those providers whether medication changes or more intensive monitoring is indicated to reduce the risk of low blood sugars and/or low blood pressures. The PI is a general internal medicine physician and will be available to answer patients' questions and/or address urgent issues, the management of all non-urgent issues will be directed to patients' existing healthcare teams.

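### Section 6.1 sets adverse event reporting aside while section 8.2 names a risk that CHIP may increase; no harm outcome is designated, systematically ascertained or analysed by arm

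*Combined protocol and SAP*

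**What the plan says.** All references are to the combined protocol and SAP.

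- **6.1 Adverse Event Reporting** consists of one sentence: "Not applicable for this minimum risk study".
- **8.2 Protection of Human Subjects Against Risks** says that CHIP may increase the "risk of medication-associated low blood sugars and/or low blood pressures, especially if patients do not adjust their medications" to allow for the programme's effects. Its response is advice and availability: "Patients will be advised to discuss their CHIP participation with their primary care providers", and the investigator is on hand for patients' "questions and/or address urgent issues, the management of all non-urgent issues will be directed to" their usual care teams.
- **5.6 Procedures** adds a discretionary exit: "The study doctor could decide to disenroll participants from this research study if they believe it is in the" participant's best interest.
- **8.1** gives a general undertaking: "The investigator will provide for the protection of the subjects by following all applicable regulations".
- **5.8 Secondary Endpoints** includes "Biometrics at 3 and 6 months: weight, body mass index, blood pressure" and "Number of diabetes medications prescribed at 3 and 6 months", as well as total cost of care.
- **5.10.1** lists claims data (number of claims and total cost, by inpatient, emergency and outpatient setting) and permits manual chart review for required data elements.
- **5.9.1** limits the analysis to the primary and secondary outcomes, recruitment and attendance, and says the estimates will feed the design of a larger study.
- **Section 7**, the second section headed Safety Monitoring, covers only blood sampling and record retention.

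**The concern.** The protocol foresees a particular harm, attributes it to the intervention, and then sets event reporting aside. Staff who follow 6.1 literally have no instruction to ask about, record or report low blood sugar or low blood pressure in either arm.

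The pilot exists to inform a larger trial. As planned, it would report the possible benefits of CHIP by arm and would give no systematic account of the one intervention-related harm it names. Planners of the larger trial would then have at best a partial, after-the-fact picture from data gathered for other purposes.

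**Working it through.** **1. Is a harm outcome specified anywhere?** Each place where one could appear:

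| Section | Content | Harm outcome? |
|---|---|---|
| 5.6 Data Collection | Biometrics, HbA1c, LDL-C, Wellbeing360, medication list | None |
| 5.6.1 tables, both arms | The same measures, without the medication list; a satisfaction survey in the CHIP arm | None |
| 5.7 Primary Endpoints | HbA1c change at 6 months; feasibility proportions | None |
| 5.8 Secondary Endpoints | HbA1c, LDL-C, biometrics, survey, attendance, medication count, cost | None |
| 5.9.1 SAP | Mean and SD of change; difference between groups; recruitment and attendance | None |
| 5.10.1 data list | Demographics, biometrics, labs, medications, claims | None |
| 7 Safety Monitoring | Blood samples, retention | None |

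**2. Do the safety provisions record events?** Investigator availability, advice to consult primary care and discretionary disenrolment are all real provisions. None is stated to produce a record.

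**3. What could the collected data show?**

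- Blood pressure is read at weeks 1, 12 and 26 in both arms. It bears directly on one of the two named harms, but only at those moments.
- Medication lists show changes in treatment, not episodes.
- Inpatient and emergency claims could show severe, billed episodes if diagnosis codes are supplied; 5.10.1 names only counts and costs, followed by an open-ended etc. Section 5.5.2 allows a 3-month claims lag.
- Mild, unbilled or between-visit episodes would be missed.

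**4. How precise would descriptive rates be?** Section 5.9.2 gives 30 per group. Its own half-widths reproduce at that size: t(0.975, 29)/√30 = 0.373 (stated 0.37) and t(0.975, 58) × √(2/30) = 0.517 (stated 0.52). The documents give no event rate, so what follows illustrates precision only.

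- Zero events in n, one-sided 95% upper bound = 1 − 0.05^(1/n). For n = 30: 1 − 0.05^(1/30) = 0.095, or 9.5%. For n = 24 (assuming 80% of 30 ascertained): 1 − 0.05^(1/24) = 0.117, or 11.7%.
- Three events in 30: 10%, exact (Clopper-Pearson) 95% CI 2.1% to 26.5%.
- Chance of seeing at least one event in an arm = 1 − (1 − p)^30. For assumed p of 1%, 2%, 5% and 10%, this is 26%, 45%, 79% and 96%.

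**5. Caveats on the remedy, not defects in the plan.** The plan proposes neither of the following analyses.

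- Exact power of a two-sided 5% Fisher test with 30 per arm is 0.093 for 5% vs 15% and 0.241 for 5% vs 20% (assumed rates). The counts could not serve as a test.
- Comparing informal reports by arm would mislead. With a true rate of 10% in both arms and assumed capture of 80% in CHIP and 40% in control, expected recorded events are 30 × 0.10 × 0.8 = 2.4 and 30 × 0.10 × 0.4 = 1.2, a false ratio of 2.0. With 80% and 60% capture it is 2.4/1.8 = 1.3.

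**The case against.** The strongest reply has four parts.

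- **No flat contradiction.** A study can be minimal risk and still name a risk. Screening also bears on that label: 5.2.3 excludes conditions that contraindicate CHIP and patients on warfarin, and 5.3 has the medical director judge whether the diet is safe when a case is not covered. This stands. What remains is a tension to reconcile, because a risk label does not say how the named events are to be recorded.
- **Harm-relevant data are collected.** A reader might infer that nothing bearing on harm is gathered, or that no harm rate could ever be described. The documents do not support that. Blood pressure, medication lists and claims are obtained in both arms, and chart review is allowed, so some count of severe events might be recovered. But no harm is listed as a required element, and the milder episodes would be lost.
- **Reporting may be covered elsewhere.** A reader might infer that no reporting route exists. That cannot be concluded: IRB policy and the consent pages are not available here, and 8.1 commits to applicable regulations. Even so, regulatory reporting would not by itself give counts ascertained in the same way in both arms.
- **The pilot is small and aims at variability and feasibility.** This also stands. Sizing the larger trial on HbA1c depends on the variability of change, not on a harm rate, and 30 per arm cannot test a difference in harms. It limits what the counts can be used for; it is not a reason to leave a foreseen harm without a plan.

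**Conclusion.** The point holds, in limited form. Sections 6.1 and 8.2 must be reconciled, and the plan designates, systematically ascertains and analyses by arm no harm outcome. This should be fixed, as a matter of safety and of the pilot's value for planning. It is not a threat to the results: no planned efficacy or feasibility estimate is biased.

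Confidence is high on the missing ascertainment and analysis, which can be checked section by section. It is lower on reporting, which may be handled in material not seen. On size, the most the pilot could offer is a descriptive rate with wide limits: up to 9.5% after zero events in 30, or 11.7% if only 24 are ascertained (an assumed 80%). It would be wrong to read the point as evidence that CHIP causes harm, or as saying that this trial could show whether it does.

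**What to change.** **Necessary:** reconcile 6.1 with 8.2, and state whether and how the foreseen events are recorded in both arms.

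**Cheap improvement.** Replace 6.1 with wording such as: *At the week 12 and week 26 data-collection contacts, participants in both arms are asked the same short scripted questions about low blood sugar and symptomatic low blood pressure since the previous contact. Anyone not asked at the visit is followed up by telephone. Serious or unanticipated events that become known are recorded and reported under IRB policy.* The telephone step should be its own provision, because the medication-reconciliation call in 5.6 is made only when a list cannot be completed at the visit and so would not reach everyone. The script should say what counts as a reported episode.

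Then:

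- Add a row for the questions to both tables in 5.6.1.
- Add to 5.8 and 5.9.1 descriptive counts and proportions by arm, with exact 95% CIs and the number ascertained.
- Optionally add claims-based emergency and inpatient counts, if diagnosis codes are available and the qualifying encounters are defined in advance.
- List informally known events separately and do not compare them by arm, because CHIP participants have 18 classes and controls have three appointments.
- State that the rates are for planning and do not test whether CHIP raises risk.

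**Cost:** a protocol amendment, a few questions, one table, some data entry and IRB reporting, and possibly a wider claims request. Recall over 12 − 1 = 11 and 26 − 12 = 14 weeks will miss mild episodes. It may also differ by arm, because participants know their allocation and CHIP participants are told to raise their participation with their providers. Because of the 3-month lag, claims cannot show a cluster of events while the classes are running. No change to clinical management is proposed.
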